## **6.2 Surgical Stay**

Patient reported pain will be measured utilizing visual analogue scales – VAS at 4 hour intervals during the duration of their inpatient hospitalization following surgery. Further, time until cessation of the nerve blockade as quantified as time to patient reported cessation of the nerve blockade, and time until first opioid rescue will be noted. Patients and nursing staff will be educated on how to accurately quantify time to patient reported cessation of the nerve blockade as follows: pain scores of 3 or greater at surgical site will be considered as time of cessation of nerve block.

Furthermore, all narcotic utilization during the hospitalization will be recorded. All values will be presented as morphine equivalents.

Operative time, laterality of surgery, length of stay, and disposition at discharge from the hospital will additionally be collected.

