### 1.1 Background

The “Opioid Crisis” has been characterized by a significant rise in the prevalence of opioid dependence and drug related deaths. Not only has this placed a substantial strain on the health care economy, but resultant government legislation has led to greater restrictions on narcotic prescriptions. Consequently, there has been increasing interest in the development of multi-modal pain control regimens, particularly, in the post-operative period.

Furthermore, in those patients undergoing orthopedic surgery, adequate pain control is highly important. Patients with poor post-operative pain management in the first 48 hours have an approximate 50 percent chance of achieving long-term satisfactory pain relief. Inadequate pain management has been shown to not only increase hospital length of stay, but increase the risk of thromboembolic events, pulmonary complications, and chronic pain. Regional analgesia through the use of local anesthetic agents is a commonly employed strategy for pain management. In shoulder surgery, specifically, peripheral nerve block with long acting local anesthetic is a well-established technique for pain control. Typical agents including bupivacaine and ropivacaine, in general, provide a block duration of 12 to 24 hours.

In 2011, liposomal bupivacaine (Exparel, Pacira Pharmaceuticals, San Diego, USA) was approved by the US Food and Drug Administration (FDA) for use as a local anesthetic for surgical site infiltration. Liposomal bupivacaine is composed of a phospholipid bilayer that encapsulates bupivacaine, extending drug delivery for up to 72 hours and potentially extending periods of regional analgesia. Early studies evaluating liposomal bupivacaine noted lower subjective pain scores, increased time to first opiate medication, and decreased opiate requirements when compared to placebo.

Liposomal bupivacaine was FDA-approved for use in interscalene nerve blocks (INB) in the setting of shoulder surgery on April 6, 2018. Despite approval, there is limited data comparing liposomal bupivacaine to traditional agents in this population. The objective of this study is to determine if peripheral nerve block with liposomal bupivacaine in combination with standard bupivacaine will prolong the duration of block, improve pain scores, and decrease opioid utilization in the post-operative period when compared to peripheral nerve block with standard bupivacaine alone.

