## 2 Study Objectives

The primary outcome measure will be:

1. Mean difference in patient pain scores over the first 72 hours post-operatively between two groups

Secondary outcomes will include:

1. Total opioid consumption (as measured utilizing morphine intravenous equivalents) in first 72 hours and at 3 weeks
2. Patient perceived duration of block determined as the time patient perceives complete resolution of block
3. Patient satisfaction with pain control at 72 hours, 3 weeks post-operatively and patient reported outcome measures (SANE, SST, ASES, VR-12) at 3 weeks post-operatively

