### 6.3 Time from discharge to first post-operative visit

At discharge, pain scores will be measured utilizing electronically managed surveys that will be e-mailed to each patient on a twice daily basis (upon waking the AM and just prior to bedtime) after discharge for the first 72 hours following surgery. Finally, patient satisfaction scores (Likert scores) will be emailed to the subjects at 72 hours.

Total opioid consumption will similarly be measured based off of electronically managed surveys or a written diary on a daily basis following discharge for the first 72 hours. All values will be presented as morphine equivalents.

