#### Multiplicity

There is only one primary hypothesis so we will not adjust for multiplicity at the highest level. However, if the linear mixed-model shows that the time by treatment interaction term is statistically significant and we perform post-hoc pairwise comparisons, the Tukey-Kramer

method will be used to adjust for multiple comparisons. There are several secondary aims that we consider exploratory analyses and as such will not adjust for multiple comparisons.

**Primary Hypothesis:** The average post-op pain score, adjusted for baseline pain scores, over the 72 hours post-op will be significantly lower in the liposomal bupivacaine group.

The difference in post-operative numeric pain scores between the treatment groups over time will be analyzed using a linear mixed-model with an interaction term for time and treatment and will adjust for the baseline (pre-op) scores.

**Secondary Hypothesis 1:** The average post-op satisfaction score over the 72 hours post-op will be significantly lower in the liposomal bupivacaine group.

The difference in post-operative numeric satisfaction scores between the treatment groups over time will be analyzed using a linear mixed-model with an interaction term for time and treatment.

**Secondary Hypothesis 2:** Time to block cessation will be longer in the liposomal bupivacaine group than the standard bupivacaine group.

The difference in time to block cessation will be analyzed between treatment groups using a two sample t-test if necessary model assumptions are met or the Wilcoxon Rank-Sum test if assumptions are not met.

**Secondary Hypothesis 3:** Total opioid consumption will be significantly lower in the liposomal bupivacaine group.

The distribution of total opioid consumption for the two groups will be compared using a multiple linear regression model with a term to adjust for baseline opioid consumption.

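### Time to block cessation has no stated method of capture after discharge and is analysed as an exact time, so the estimated prolongation can be distorted by several hours in either direction

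*Combined protocol and SAP*

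**What the plan says.** Section 2 lists block duration as a secondary outcome: "Patient perceived duration of block determined as the time patient perceives complete resolution of block". Section 6.2 describes the variable as "quantified as time to patient reported cessation of the nerve blockade" and then attaches a threshold to it: "pain scores of 3 or greater at surgical site will be considered as time of cessation of nerve block". The same section says "Patients and nursing staff will be educated on how to accurately quantify time to patient reported cessation of the nerve blockade".

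Pain in hospital is scored by "VAS at 4 hour intervals during the duration of their inpatient hospitalization following surgery". Section 6.3 changes the frequency: surveys are "e-mailed to each patient on a twice daily basis (upon waking the AM and just prior to bedtime) after discharge", and they stop 72 hours after surgery. For the home period that section names pain, opioid use and satisfaction, but no time at which the block ended. The schedule of events in Section 6.5 has no row for it either. The next planned pain score is at the 3-week visit.

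For Secondary Hypothesis 2, Section 7.2 states: "The difference in time to block cessation will be analyzed between treatment groups using a two sample t-test", with the Wilcoxon rank-sum test if assumptions fail. It gives no censoring rule. The general last-observation-carried-forward rule does not supply a cessation time for a patient whose block has not ended.

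**The concern.** After discharge, the only specified data to which the threshold in Section 6.2 can be applied are two scores a day. If those scores date the event, a block that ends between surveys is recorded at the next one, and a block that ends after the last survey is not recorded at all.

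Both effects can fall unequally on the two arms. Section 1.1 says that typical agents "provide a block duration of 12 to 24 hours" and that liposomal bupivacaine extends drug delivery for up to 72 hours. With a short hospital stay, control blocks would tend to end on the 4-hourly grid, while longer liposomal blocks would end on the coarse home grid or beyond the window. The estimated prolongation and its confidence interval would then depend partly on when surveys are sent. Prolonging the block is the first aim named in the study objective in Section 1.1, so this estimate will be read closely even though it is secondary.

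**Working it through.** The documents give no expected difference, standard deviation or sample size for this endpoint, so there is no planned figure to reproduce. The check is of the size of the recording error.

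**Inputs from the documents.** Threshold of 3 or more and 4-hourly scores in hospital (6.2); waking and bedtime scores after discharge, ending at 72 h (6.3); standard blocks of 12 to 24 h (1.1); t-test or Wilcoxon test (7.2).

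**Assumed, because the documents do not give them.** Length of stay, liposomal block duration, survey clock times, and that the first scheduled score after the true crossing is the recorded time.

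**Step 1: mean delay on a fixed grid.** For an event falling at random in a cycle of gaps g, the mean delay to the next score is Σg² / (2 × Σg).

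- In hospital, gaps of 4 h: 4² / (2 × 4) = 2.0 h.
- At home, gaps of 12 h and 12 h: (144 + 144) / 48 = 6.0 h.
- Gaps of 14 h and 10 h: (196 + 100) / 48 = 6.2 h.
- Gaps of 15 h and 9 h: (225 + 81) / 48 = 6.4 h.
- Gaps of 16 h and 8 h: (256 + 64) / 48 = 6.7 h.

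The largest difference in mean delay between arms arises when every control block ends in hospital and every liposomal block ends at home: 6.0 − 2.0 = 4.0 h to 6.7 − 2.0 = 4.7 h.

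**Step 2: both grids and the 72-hour limit together.** A simulation with 400,000 patients per arm dated each block at the first scheduled score at or after its true end. Assumptions: surgery ending between 10:00 and 17:00; home surveys at 07:00 and 22:00; control duration normal with mean 18 h and SD 4 h; liposomal mean 18, 24, 36, 48 or 60 h with SD 4, 8, 12, 14 or 16 h. The bias is the recorded minus the true difference between arms. The first figure in each cell drops patients with no qualifying score by 72 h; the second sets them to 72 h.

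| True difference | Discharge at 24 h | Discharge at 48 h | Discharge at 72 h |
|---|---|---|---|
| 0 h | 0.0 / 0.0 | 0.0 / 0.0 | 0.0 / 0.0 |
| 6 h | +1.3 / +1.3 | 0.0 / 0.0 | 0.0 / 0.0 |
| 18 h | +2.8 / +3.0 | +0.2 / +0.5 | −0.1 / 0.0 |
| 30 h | +0.5 / +2.8 | −1.7 / +0.8 | −1.4 / −0.3 |
| 42 h | −6.4 / −0.5 | −7.9 / −1.4 | −6.3 / −2.6 |

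With discharge at 24 h, the overstatement is 1.3 / 6 = 22% of a true 6 h, and 2.8 / 18 = 16% to 3.0 / 18 = 17% of a true 18 h. At a true 42 h, 36.7% of liposomal patients have no qualifying score by 72 h, and truncation outweighs the delay.

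**The case against.** The strongest reply is that the documents never say cessation is read from the scheduled scores. Section 6.2 introduces it in a separate sentence from the 4-hourly scoring, calls it patient reported, and has patients as well as nurses trained to quantify it. Section 2 speaks of the patient's own perception, and Section 4.1 asks for patients able to complete surveys or keep a diary. A patient who notes a clock time incurs no grid delay. This stands, and it rules out saying that every recorded time must be late. It does not close the gap: the training sentence sits under the surgical stay and ties the report to a pain score, and nothing names a cessation entry in the home survey or diary.

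A reader might also infer that the plan inflates the liposomal benefit. The documents do not support that. Length of stay is only collected as data, drug delivery of up to 72 hours is not block duration, and the table shows bias near zero with longer stays and negative bias when many blocks outlast the window.

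Nor does the grid create a false difference: both arms share it, and the bias is zero under the null. Section 7.2 treats secondary aims as exploratory, and the primary pain analysis is untouched. These points limit the importance of the problem, but they do not show that the planned analysis suits the data.

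**Conclusion.** The concern holds in conditional form. As written, cessation after discharge is either not captured or can be dated only to the next twice-daily survey, and the analysis makes no allowance for that or for blocks unresolved at 72 h.

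If scheduled scores date the event, a real prolongation can be overstated by up to about 4 to 4.7 h, the limit reached when control blocks end in hospital and liposomal blocks end at home. In the assumed scenarios the net bias ran from about +3 h to about −8 h. Because length of stay, liposomal block duration and the handling of unresolved blocks are not given, neither the sign nor the size can be fixed from the documents, and a claim of certain inflation would go too far. The matter affects one exploratory secondary estimate and its interval. It is still worth correcting, because the remedy is cheap and does not depend on which way the bias runs.

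**What to change.** 1. **Capture.** Add one item to the existing morning and evening e-survey, to the written diary and to the inpatient record, asking for the clock time at which the block ended. Use that time where it is given, and add the item to the schedule of events.
2. **Analysis.** In Section 7.2, Secondary Hypothesis 2, replace the t-test or Wilcoxon test with a time-to-event analysis, such as an interval-censored log-rank test or a parametric interval-censored model. Where no clock time is given, the interval runs from the last observation before cessation to the first at or after it. Blocks unresolved at the last observation are right-censored there, rather than dropped or set to 72 h.
3. **Definition.** Reconcile Section 2 (perceived complete resolution) with Section 6.2 (pain of 3 or more), so that the clock time and the interval bounds rest on one definition.

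The cost is one extra survey item, a change of SAP wording, slightly more analysis work and possibly a somewhat wider confidence interval. If clock times are well completed, interval censoring will matter for few patients, but right censoring will still be needed for unresolved blocks.

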### 6.3 Time from discharge to first post-operative visit

At discharge, pain scores will be measured utilizing electronically managed surveys that will be e-mailed to each patient on a twice daily basis (upon waking the AM and just prior to bedtime) after discharge for the first 72 hours following surgery. Finally, patient satisfaction scores (Likert scores) will be emailed to the subjects at 72 hours.

Total opioid consumption will similarly be measured based off of electronically managed surveys or a written diary on a daily basis following discharge for the first 72 hours. All values will be presented as morphine equivalents.

### 6.4 First Post-operative Visit (3-weeks post-op)

During the first follow-up visit, total opioid consumption during their post-operative course will be measured, and pain scales and satisfaction scores will be obtained including ASES, SST, SANE, VR-12. Total opioid consumption will be quantified by the number of narcotic prescription pills remaining. Opioid consumption will be standardized to morphine equivalents. All diaries will be collected at this time.

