### **5.5 Prior and Concomitant Therapy**

All patients will receive no more than 4 mg of midazolam for sedation at the time of the block. All patients will undergo general endotracheal anesthesia using propofol, fentanyl, rocuronium or succinylcholine, sevoflurane in air-oxygen, and ondansetron. Fentanyl will be limited to 250 micrograms intraoperatively. Reversal of muscle relaxant will be with either neostigmine and glycopyrrolate or sugammadex. Block success will be assessed pre-operatively with shoulder abductor weakness and re-assessed on arrival to PACU. Patients will receive a standardized post-operative pain management regimen for 24 hours from PACU arrival.

On the post-operative floor the pain regimen will be standardized according to department protocol as follows:

- Acetaminophen 1000mg Q8 hours scheduled
- Tramadol 50mg Q6 hours PRN pain scale 4-6 with repeat dose
- Tramadol 100mg Q6 hours PRN pain scale 7-10 with repeat dose
- Oxycodone 5mg Q4 hours PRN pain scale 4-6 with repeat dose for pain not controlled with tramadol
- Oxycodone 10mg Q4 hours PRN pain scale 7-10 for pain not controlled with tramadol
- IV Fentanyl 25 mcg Q2hr PRN pain scale 7-10 with repeat dose for pain not controlled with above

Discharge medications will include one of the following options:

1. Oxycodone 5 or 10 mg Q4 hrs PRN for moderate (5-6) to severe (7-10) pain
2. Oxycodone-acetaminophen 5/325 or 10/325 Q4 hrs PRN for moderate (5-6) to severe (7-10) pain, not to exceed 8/day
3. Hydrocodone-acetaminophen 5/325 or 10/325 Q4 hrs PRN for moderate (5-6) to severe (7-10) pain, not to exceed 8/day
4. Tramadol 50 mg or 100 mg Q6 hrs PRN for moderate (5-6) to severe (7-10) pain, not to exceed 6/day
5. Tylenol 1000 mg q6hr PRN pain moderate to severe pain, total dose not to exceed 4000 mg/day

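### The 3-week opioid total is defined by pills remaining, a rule with no term for inpatient opioids, quantity dispensed or refills, so as written it does not measure consumption over the post-operative course

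*Combined protocol and SAP*

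**What the plan says.** Section 2 lists as a secondary outcome "Total opioid consumption (as measured utilizing morphine intravenous equivalents) in first 72 hours and at 3 weeks". The data come from three places.

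- **Hospital stay (section 6.2):** "all narcotic utilization during the hospitalization will be recorded". The ward regimen in section 5.5 includes tramadol, oxycodone and, as a further step, "IV Fentanyl 25 mcg Q2hr PRN pain scale 7-10".
- **Discharge to 72 hours (section 6.3):** use is taken from "electronically managed surveys or a written diary on a daily basis following discharge for the first 72 hours".
- **3-week visit (section 6.4):** the scope is that "total opioid consumption during their post-operative course will be measured", and the method is "Total opioid consumption will be quantified by the number of narcotic prescription pills remaining". The result is to be expressed in morphine equivalents.

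On what patients take home, section 5.5 says "Discharge medications will include one of the following options" and lists five. Four contain an opioid (oxycodone, oxycodone-acetaminophen, hydrocodone-acetaminophen, tramadol), each in two strengths. The fifth is acetaminophen alone. No quantity is given and refills are not mentioned.

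The schedule in section 6.5 marks opioid use at the surgical stay, after discharge and at the post-operative visit. It marks concurrent medications only before surgery. Section 7.2, Secondary Hypothesis 3, compares total opioid consumption by linear regression adjusted for baseline use, without naming the window. The same section treats the secondary aims as exploratory.

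**The concern.** The scope and the method in section 6.4 do not match. A count of leftover prescription pills says nothing about doses given from ward stock, and it turns into consumption only after subtraction from what was dispensed. After 72 hours no survey or diary of opioid use is planned, so the pill count is the only stated source for the rest of the three weeks.

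The error need not be equal between arms. The trial's hypothesis is that the liposomal arm uses less opioid. If control patients take more in hospital or refill more often, the parts left out are larger in the control arm, and the 3-week comparison understates the effect the trial is looking for. There is also a practical risk: dispensed quantities that are not recorded at the time may be hard to recover later.

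**Working it through.** The plan states no figure on this point, so there is none to reproduce. The check is bookkeeping on the rule as written. All patient-level counts below are assumptions, in 5 mg oxycodone tablets with 30 in the first fill.

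**Step 1. Is the count enough by itself?** Suppose 15 pills of oxycodone remain. Section 5.5 allows 5 or 10 mg.
- 30 dispensed, 5 mg: (30 − 15) × 5 = 75 mg.
- 30 dispensed, 10 mg: (30 − 15) × 10 = 150 mg.
- 30 plus a refill of 30, 5 mg: (60 − 15) × 5 = 225 mg.
- 30 plus a refill of 30, 10 mg: (60 − 15) × 10 = 450 mg.

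The same count fits 75 to 450 mg. Likewise, no narcotic pills remaining could mean that all were used or that none were prescribed (the acetaminophen option).

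**Step 2. Size of the shortfall per patient.** Let H be inpatient mg and R the pills in a refill that is not counted.
- Pill-count total = (first fill − remaining) × 5.
- Full total = H + (first fill + R − remaining) × 5.
- Shortfall = H + 5R.

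| Assumed patient | H (mg) | Pills to 72 h | Pills later | R | Remaining | Pill-count total | Full total | Shortfall |
|---|---|---|---|---|---|---|---|---|
| A | 20 | 0 | 0 | 0 | 30 | 0 | 20 | 20 |
| B | 20 | 6 | 2 | 0 | 22 | 40 | 60 | 20 |
| C | 20 | 6 | 10 | 0 | 14 | 80 | 100 | 20 |
| D | 40 | 12 | 33 | 30 | 15 | 75 | 265 | 190 |
| E | 40 | 12 | 18 | 30 | 30 | 0 | 190 | 190 |

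In D and E, 40 mg of the shortfall is inpatient use and 30 × 5 = 150 mg is the refill. If the refill is added to the dispensed count, only the 40 mg is missing.

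**Step 3. Effect on the group difference.** Measured difference (control minus liposomal) = true difference − (mean shortfall in control − mean shortfall in liposomal). Equal mean shortfalls leave the difference unbiased. A larger one in control pulls it toward zero when control truly uses more. With one uncounted 30-pill refill worth 150 mg, each 10 percentage points by which control refills exceed liposomal refills removes 0.10 × 150 = 15 mg, on top of any difference in mean H.

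**Step 4. Does the 3-week total fall below the 72-hour total?** It depends on what is added to each window.

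| Patient | Outpatient only: 72 h / 3 wk | Hospital added to both: 72 h / 3 wk | Hospital added to 72 h only: 72 h / 3 wk |
|---|---|---|---|
| A | 0 / 0 | 20 / 20 | 20 / 0 |
| B | 30 / 40 | 50 / 60 | 50 / 40 |
| C | 30 / 80 | 50 / 100 | 50 / 80 |
| D | 60 / 75 | 100 / 115 | 100 / 75 |
| E | 60 / 0 | 100 / 40 | 100 / 0 |

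The 3-week column here uses first fill minus remaining. With both windows built alike, only E reverses, and there the cause is the uncounted refill. With refills counted and hospital doses in both windows, the 3-week totals are 20, 60, 100, 265 and 190 mg, none below its 72-hour value.

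**The case against.** The strongest reply is that section 6.4 should be read with its neighbours. It names the whole post-operative course, section 6.2 captures every inpatient dose, and the schedule marks opioid use in all three post-operative periods. On that reading the pill count supplies only the outpatient part. Converting to morphine equivalents presupposes knowing the drug, strength and quantity dispensed, so those items are arguably implied. The case report form is not part of the documents and may hold the fields.

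Much of this stands. Inpatient data are not lost, and competent staff could assemble the right total. But the reading supplies an addition and a subtraction that no section states, while the one rule that is stated gives something else.

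Three stronger readings are tempting and are not supported.
- A reader might infer that the 3-week total will generally come out below the 72-hour total. Without a refill error, that needs hospital doses in one window and not the other. No section states the sum for either window, and section 6.3 describes its 72-hour measure in terms of surveys and diaries alone.
- A reader might infer that every refill spoils the count. It does so only if the refill is left out of the quantity dispensed, on which the documents are silent. A case such as E without any use of the refill beyond the first fill's worth may also show itself at the visit.
- A reader might infer that the heaviest users are missed. A heavy user who finishes one prescription without a refill has outpatient use counted correctly, and the documents give no refill rate.

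**Conclusion.** The point holds in a limited form: the stated 3-week rule does not measure the stated quantity. It has no term for inpatient opioids, and it understates use in patients who refill unless refills are added to a dispensed quantity that no section says is recorded.

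The shortfall per patient is inpatient use plus any uncounted refill. The 20 to 190 mg range rests wholly on the assumed counts. Bias toward zero in the group comparison requires that inpatient use or uncounted refills be greater in the control arm; that is plausible under the trial's hypothesis, but its size cannot be estimated from the documents.

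The consequence is confined to one window of a secondary outcome that the plan treats as exploratory. The primary pain outcome and the sample size are untouched. This is a minor correction, worth making because reduced opioid use is one of the trial's stated aims.

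**What to change.** - In section 6.4, define the 3-week total as recorded inpatient opioids plus (all opioid units dispensed through the 3-week visit, including refills and outside prescriptions, minus units remaining), computed by drug and strength.
- Use the same inpatient-plus-outpatient construction for the 72-hour total, with the survey or diary as the outpatient part.
- State one morphine-equivalent unit for both. Section 2 names intravenous equivalents, whereas the conversion source cited in section 6.2 is titled as oral equivalents.
- In Secondary Hypothesis 3, say which window, or both, the regression uses.
- Add a data check that each patient's 3-week total is not below the 72-hour total.

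The cost is a few more case report form fields at a visit that already takes place (each fill and refill by drug, strength and quantity, plus units remaining), filled from the prescription record and a question to the patient about other prescriptions. Outside prescriptions will depend partly on patient report, so some error will remain.
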